Pembrolizumab may cause severe or life-threatening infusion-reactions including severe hypersensitivity or anaphylaxis. Signs and symptoms usually develop during or shortly after drug infusion and generally resolve completely within 24 hours of completion of infusion. Dose modification and toxicity management guidelines for irAEs and infusion reactions associated with pembrolizumab are provided in Section 8.3b, Table 2, below.

NOTE that non-irAEs will be managed as appropriate, following clinical practice recommendations.

a. Dose Modification and Toxicity Management for Immune-related Adverse Events Associated with Pembrolizumab

Table 1 Dose Modification and Toxicity Management Guidelines for Immune-related AEs and Infusion Reactions Associated with Pembrolizumab

General instructions:

- 1. For non-endocrine-related severe and life-threatening irAEs, investigators should consider the use of IV corticosteroids followed by oral steroids. Other immunosuppressive treatment should begin if the irAEs are not controlled by corticosteroids. Some non-endocrine irAEs do not require steroids. For example, celiac disease induced by pembrolizumab can be controlled by diet alone.
- 2. For non-endocrine-related toxicities, pembrolizumab must be permanently discontinued if the irAE does not resolve or the corticosteroid dose is not ≤10 mg/day within 12 weeks of the last pembrolizumab-treatment.
- 3. Generally, when corticosteroids are used, investigators should begin a taper when the irAE is ≤Grade 1 and continue at least 4 weeks.
- 4. If pembrolizumab has been withheld due to a non-endocrine irAE, pembrolizumab may generally resume after the irAE has decreased to ≤Grade 1 after a corticosteroid taper.

	irA	Toxicity grade	Action with	Corticosteroid and/or	
	Es	(CTCAE V5.0)	pembrolizuma b	other therapies	Monitoring and follow-up
ı C	one in a second	Recurrent Grade 2, Grade 3 or 4	Permanently discontinue	Administer corticosteroids (initial dose of 1 to 2 mg/kg prednisone or equivalent) followed by taper Add prophylactic antibiotics for opportunistic infections	Monitor participants for signs and symptoms of pneumonitis Evaluate participants with suspected pneumonitis with radiographic imaging and initiate corticosteroid treatment

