- ^b AST/ALT: >5.0 to 20.0 x ULN, if baseline normal; >5.0 to 20.0 x baseline, if baseline abnormal; bilirubin:>3.0 to 10.0 x ULN if baseline normal; >3.0 to 10.0 x baseline abnormal
- AST/ALT: >20.0 x ULN, if baseline normal; >20.0 x baseline, if baseline abnormal; bilirubin: >10.0 x ULN if baseline normal; >10.0 x baseline if baseline abnormal
- The decision to withhold or permanently discontinue pembrolizumab is at the discretion of the investigator or treating physician. If control achieved or ≤Grade 2, pembrolizumab may be resumed.
- ^e Events that require discontinuation include but are not limited to: encephalitis and other clinically important irAEs (e.g. vasculitis and sclerosing cholangitis).

Appropriate resuscitation equipment should be available at the bedside and a physician readily available during the period of drug administration. For further information, please refer to the Common Terminology Criteria for Adverse Events v5.0 (CTCAE) at http://ctep.cancer.gov.

b. Management of Infusion Reactions

• Signs and symptoms usually develop during or shortly after drug infusion and generally resolve completely within 24 hours of completion of infusion.

Table 2 below shows treatment guidelines for patients who experience an infusion reaction associated with administration of pembrolizumab (MK-3475).

Table 2 Pembrolizumab (MK-3475) Infusion Reaction Treatment Guidelines

Infusion Reactions	NCI CTCAE Grade	Treatment	Premedication at subsequent dosing
Mild reaction; infusion interruption not indicated; intervention not indicated	Grade 1	Increase monitoring of vital signs as medically indicated until the participant is deemed medically stable in the opinion of the investigator.	None

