Life-threatening; pressor or ventilator support indicated	Grade 4	Admit participant to intensive care unit (ICU) and initiate hemodynamic monitoring, mechanical ventilation, and/or IV fluids and vasopressors as needed. Monitor other organ function closely. Manage constitutional symptoms and organ toxicities as per institutional practice. Follow Grade 3 recommendations as applicable.	No subsequent dosing.

Appropriate resuscitation equipment should be available at the bedside and a physician readily available during the period of drug administration. For further information, please refer to the Common Terminology Criteria for Adverse Events v5.0 (CTCAE) at http://ctep.cancer.gov.

c. Management of Neurological Toxicities

Table 3 Neurological Toxicities

Event	Management
Immune-mediated	Continue pembrolizumab.
neuropathy, Grade	Investigate etiology.
1	 Any cranial nerve disorder (including facial paresis) should be managed as per Grade 2 management guidelines below.
Immune-mediated	Withhold pembrolizumab for up to 12 weeks after event onset. a
neuropathy,	 Investigate etiology and refer patient to neurologist.
including facial	 Initiate treatment as per institutional guidelines.
paresis, Grade 2	For general immune-mediated neuropathy:
	 If event resolves to Grade 1 or better, resume pembrolizumab.
	 If event does not resolve to Grade 1 or better while withholding
	pembrolizumab, permanently discontinue pembrolizumab. c
	For facial paresis:
	o If event resolves fully, resume pembrolizumab. b
	o If event does not resolve fully while withholding pembrolizumab, permanently
1 1 1	discontinue pembrolizumab. c
Immune-mediated	Permanently discontinue pembrolizumab. ^c
neuropathy,	Refer patient to neurologist. Nitiate treatment as per institutional guidelines.
including facial	Initiate treatment as per institutional guidelines.
paresis, Grade 3	
or 4	
Myasthenia gravis	Permanently discontinue pembrolizumab. ^c
and Guillain-Barré	Refer patient to neurologist.
syndrome (any	Initiate treatment as per institutional guidelines.
grade)	Consider initiation of corticosteroids equivalent to 1–2 mg/kg/day oral or IV
	prednisone.

prednisone before pembrolizumab can be resumed.

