^c Resumption of pembrolizumab may be considered in patients who are deriving benefit and have fully recovered from the immune-mediated event. The decision to re-challenge patients with pembrolizumab should be based on investigator's assessment of benefit-risk and documented by the investigator (or an appropriate delegate).

Event	Management
Immune-mediated myelitis, Grade 1	 Continue pembrolizumab unless symptoms worsen or do not improve. Investigate etiology and refer patient to a neurologist.
Immune-mediated myelitis, Grade 2	 Permanently discontinue pembrolizumab. Investigate etiology and refer patient to a neurologist. Rule out infection. Initiate treatment with corticosteroids equivalent to 1-2 mg/kg/day oral prednisone.
Immune-mediated myelitis, Grade 3 or 4	 Permanently discontinue pembrolizumab. Refer patient to a neurologist. Initiate treatment as per institutional guidelines.

Event	Management
Immune-mediated	Permanently discontinue pembrolizumab. a
meningoencephalitis, all	Refer patient to neurologist.
grades	Initiate treatment with corticosteroids equivalent to 1–2 mg/kg/day IV
	methylprednisolone and convert to 1–2 mg/kg/day oral prednisone or equivalent
	upon improvement.
	If event does not improve within 48 hours after initiating corticosteroids,
	consider adding an immunosuppressive agent.
	 If event resolves to Grade 1 or better, taper corticosteroids over ≥1 month.

^a Resumption of pembrolizumab may be considered in patients who are deriving benefit and have fully recovered from the immune-mediated event. The decision to re-challenge patients with pembrolizumab should be based on investigator's assessment of benefit–risk and documented by the investigator (or an appropriate delegate).

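### Tables 1 and 3 of Section 8.3 count the 12-week limit for Grade 2 immune-mediated neuropathy from different dates, and differ on whether a permanent stop for serious neurologic irAEs can be reversed

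*Combined protocol and SAP*

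**What the plan says.** **Table 1 (Section 8.3a).** General instruction 2 reads "For non-endocrine-related toxicities, pembrolizumab must be permanently discontinued if the irAE does not resolve". It adds a second trigger, a steroid dose still above 10 mg/day, and its time limit is "within 12 weeks of the last pembrolizumab-treatment". The only toxicities outside its scope are endocrine ones. In the All Other irAEs row, Grade 4 and recurrent Grade 3 events are to be permanently discontinued. A Grade 3 event that is not recurrent may be withheld or discontinued, with a pointer to footnote e: "Events that require discontinuation include but are not limited to: encephalitis and other clinically important irAEs". Neither the row nor the footnote shows a route back to treatment.

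**Table 3 (Section 8.3c).** For Grade 2 immune-mediated neuropathy, including facial paresis, the instruction is "Withhold pembrolizumab for up to 12 weeks after event onset". For general neuropathy it continues "If event resolves to Grade 1 or better, resume pembrolizumab"; facial paresis must resolve fully. Permanent discontinuation is the instruction for Grade 2 events that do not recover, Grade 3 or 4 neuropathy, and any grade of myasthenia gravis or Guillain-Barré syndrome (all with footnote c), and for any grade of meningoencephalitis (footnote a of that part). Both footnotes then say "Resumption of pembrolizumab may be considered in patients who are deriving benefit and have fully recovered from the immune-mediated event". Footnote c adds "The decision to re-challenge patients with pembrolizumab should be based on investigator's assessment of benefit-risk and documented by the investigator", and footnote a says the same.

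**Cross-references.** Sections 7.1 and 8.2b send the reader to 8.3a. Section 8.3 refers to Tables 1 and 2. None of them names 8.3c or Table 3, and the readable text states no order of precedence between the tables.

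**The concern.** Immune-mediated neuropathy is a non-endocrine irAE, so a Grade 2 case falls under both instruction 2 and its own row in Table 3. The two rules allow the same length of time but start the count on different dates, and they lead to incompatible actions: a mandatory permanent stop or resumption.

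The second difference concerns the word permanent. In Table 1 it is unqualified. In the footnoted rows of Table 3 it is a default that the investigator may reverse after full recovery.

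These events are foreseen. The adverse event list in Section 3.1 includes Guillain-Barré syndrome, myasthenic syndrome, peripheral motor neuropathy and non-infectious encephalitis among rare but serious events. At stake is consistent dosing after a serious immune event. Consistent off-treatment reasons (Section 7.8) and the safety and tolerability objective of both cohorts (Section 1.2) are also touched, to a lesser degree.

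**Working it through.** The plan gives no figure to reproduce. The check is date arithmetic for the clocks and a side-by-side reading for re-challenge.

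**Clocks: inputs**
- Table 1 limit: 12 weeks × 7 = 84 days from the last dose (8.3a, instruction 2).
- Table 3 limit: 84 days from event onset (8.3c, Grade 2 neuropathy row).
- Cycle length 21 days, with dosing allowed up to 3 days late for administrative reasons (Section 7.2). The longest on-schedule gap from dose to onset is therefore 21 + 3 = 24 days.

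Let d be the days from last dose to onset of the Grade 2 event. Counted from the last dose, Table 1 closes on day 84 and Table 3 on day 84 + d. The gap is d.

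| d (days) | Table 1 limit | Table 3 limit | Table 3 limit, weeks after last dose |
|---|---|---|---|
| 0 | day 84 | day 84 | 12.0 |
| 7 | day 84 | day 91 | 13.0 |
| 14 | day 84 | day 98 | 14.0 |
| 21 | day 84 | day 105 | 15.0 |
| 24 | day 84 | day 108 | 108/7 = 15.4 |

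**Worked case.** Onset is on day 20, the event is still Grade 2 on day 84, and it reaches Grade 1 on day 95.
- From the last dose: 95/7 = 13.6 weeks, past 12, so Table 1 requires permanent discontinuation.
- From onset: (95 − 20)/7 = 75/7 = 10.7 weeks, within 12, so Table 3 says resume (general neuropathy).

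A case that recovers by day 84 meets both time limits. One that has not recovered by day 84 + d is stopped under both. The clock conflict lies only between those days.

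**Re-challenge: side by side**

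| Event | Table 1 | Table 3 |
|---|---|---|
| Grade 4 neuropathy, myasthenia gravis or Guillain-Barré syndrome, or recurrent Grade 3 (via All Other irAEs) | Permanent discontinuation, no exception shown | Permanent discontinuation; resumption may be considered (footnote c) |
| Encephalitis / meningoencephalitis | Discontinuation required (footnote e), no exception shown | Permanent discontinuation; resumption may be considered (footnote a) |
| Grade 3, not recurrent | Withhold or discontinue | Permanent discontinuation; resumption may be considered (footnote c) |

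The first two rows differ on whether treatment can restart. The third does not, because Table 1 itself leaves room to withhold and resume.

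**The case against.** **The specific table governs.** This is the strongest reply: Table 3 is written for neurologic events, so it displaces the general instruction. It is a reasonable reading, but the readable text does not say so. Table 1 names a neurologic event in footnote e, so it does not leave neurology to Table 3. Instruction 2 says must, where instructions 3 and 4 use generally. The cross-references also do not lead to Table 3.

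**The 12-week line carries a footnote.** It is marked a, and only a fragment of that part's early footnotes is readable, on prednisone before resumption. Footnote a may qualify the line. That stands as a condition on the clock finding.

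**The default actions largely agree.** Both tables stop treatment for Grade 4 events and for encephalitis, and footnote e does not use the word permanent. The Table 3 footnotes are permissive and require benefit, full recovery and documentation. This narrows the second conflict to whether a restart is ever allowed, but does not remove it.

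**Stronger readings that the documents do not support.**
- A reader might infer that every neurologic irAE draws opposite instructions. The 12-week onset clock appears only in the Grade 2 neuropathy row, and conflicts only for recovery between the two limits.
- A reader might infer that resumption contradicts required surgery in Cohort A. A footnote saying that resumption may be considered does not override Sections 7.2b and 7.3.
- Section 8.3 says irAEs may arise several months after the last dose, which might suggest a much larger gap. With three-weekly dosing and interruptions normally limited to 3 weeks (Section 8.2c), such patients will mostly be off treatment already, so the choice to resume seldom arises.
- Nothing shows that patients will be re-dosed at one site and stopped at another, only that they can be. Re-challenge rests on investigator judgement, so some variation would remain after any rewording.

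**Conclusion.** The concern holds in a limited form. For Grade 2 immune-mediated neuropathy or facial paresis, the two 12-week limits differ by d days, up to 24 on schedule, so that Table 3 can run to about 15.4 weeks after the last dose against 12 in Table 1. Recovery inside that window meets incompatible instructions. Separately, permanent discontinuation means different things in the two tables for Grade 4 or recurrent Grade 3 neurologic events and for encephalitis or meningoencephalitis.

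This rests on four assumptions:
- The 12-week phrase in instruction 2 applies to resolution of the irAE as well as to the steroid dose.
- The partly legible footnote a does not already settle the anchor date.
- The All Other irAEs row covers neurologic events that Table 1 does not list by name.
- Encephalitis in footnote e and meningoencephalitis in Table 3 overlap.

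Exposure is mainly in Cohort B, with up to 34 cycles; Cohort A has three and a possible fourth. Few patients would be affected. Neither primary endpoint is shown to be affected, and the toxicity analysis in Section 11.1d estimates occurrence rates rather than discontinuation rates. The point merits correction because two stated rules give incompatible dosing actions after a serious event.

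**What to change.** The sponsor should reconcile general instruction 2, the All Other irAEs row and footnote e of Table 1 with Table 3 and its footnotes, so that neurologic irAEs have:
- one anchor date for the 12-week limit;
- one stated meaning of permanent discontinuation, including whether resumption can be considered.

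Sections 7.1, 8.2b and 8.3 should also cross-reference 8.3c. The sponsor should check first whether footnote a to the 12-week line already resolves the anchor date. Which date and which re-challenge rule should apply is a clinical decision for the sponsor and NCI, and no view is taken here.

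The cost is a short clarification sent to sites, with no new data, visits or procedures.

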8.4 Use of Transfusion and/or EPO

Transfusions and/or erythropoietin may be utilized as clinically indicated for the treatment of anemia, but should be clearly noted as concurrent medications. Transfusion of platelets may be used if clinically indicated. ITP should be ruled out before initiation of platelet transfusion.

8.5 Use of G-CSF

Prophylactic use of colony-stimulating factors including Granulocyte Colony-Stimulating Factor (G-CSF), pegylated G-CSF or Granulocyte Macrophage Colony-Stimulating Factor GM CSF is not allowed in this study. Therapeutic use of G-CSF is allowed in patients with Grade 3-4 febrile neutropenia.

8.6 Anti-Infectives

Patients with a documented infectious complication should receive oral or IV antibiotics or other anti-infective agents as considered appropriate by the treating Investigator for a given infectious condition, according to standard institutional practice.

8.8 Adverse Event Reporting

Toxicities (including suspected reactions) that meet the expedited reporting criteria as outlined in Section:16.1 of the protocol must be reported to the Operations Office, Study Chair and NCI via CTEP-AERS, and to the IRB per local IRB requirements.

9.0 STUDY CALENDAR

9.1 Pembrolizumab (MK-3475)-Cohort A

REQUIRED STUDIES	Pre-study (screening) ^t	ON TREATMENT Each cycle consists of 1 infusion. Infusions to be given q 3 weeks. aq Cycle 1 Cycle 2 Cycle 3 Possible Cycle 4 Week 1* Week 4* Week 7* Week 10*			End of Treatment assessment ^u	Surgical Resection ^s	Post treatment F/U prior to progression/ relapse ^c	Post treatment F/U post- progression/ relapse ^d	
PHYSICAL					2	0,			
History & Physical, PS (w/BP &Weight) ^r	Х	Х	Х	Х	х	Х		Х	Х
Adverse Event Notation			Х	X	X	X p		Χþ	Χþ
Baseline Abnormalities	Х	Х							
Skin exam ^p	Х	Х	Х	Х	Х	Χq		Х	
LABORATORY ^e									
ANC, platelets, Hgb	Х	Х	X	Х	Х	Х		Х	
Total bilirubin	Х	Х	X	Х	Х	Х		Х	
LDH ^f	X								Х
AST and ALT, Alkaline Phosphatase	Х	X	X	Х	Х	Х		X	
Serum Creatinine or CrCl	X	X	Х	Х	Х	X		X	
Albumin, Glucose, Na, K, HCO3/CO ₂	S	х	×	×	X	x		x	
Thyroid function test °		Х		Х				Х	X
Pregnancy test ⁱ	×	Χ	Χ	Χ	Х	X			

Study Calendar 9.1 continued on next page. Click here for footnotes.

REQUIRED STUDIES	Pre-study ^t (screening)	ON TREATMENT Each cycle consists of 1 infusion. Infusions to be given q 3 weeks. ^{a q}				End of treatment	Surgical resection s	Post treatment F/U prior to	Post treatment F/U post
		Cycle 1	Cycle 2	Cycle 3	Possible Cycle 4	assessment	0	progression/ relapse ^c	progression/ relapse ^d
		Week 1 *	Week 4 *	Week 7 *	Week 10				
X-RAYS AND SCANS						ON,			
CT ^j , chest, abdomen & pelvis or whole body PET/CT	Х				Χq	X y q		X ^k	Χv
EKG ^h	Х				. ()				
Brain MRI or CT with contrast h	Х			· ·	(/,				
SPECIMEN SUBMISSION					1				
Tissue X	X		Χ				X		X (optional)
Whole Blood w	Х								
TREATMENT									
Pembrolizumab (MK- 3475) ^a		Х	X	X	Χq				

Click here for footnotes.

NOTE: Forms are found on the protocol abstract page of the SWOG website (www.swog.org). Form submission guidelines are found in Section 14.0.

NOTE: Unless indicated otherwise in the protocol, scheduled procedures and assessments (treatment administration, toxicity assessment for continuous treatment, disease assessment, specimen collection and follow-up activities) must follow the established SWOG guidelines as outlined in https://swog.org/Visitors/Download/QA/best%20Practices%20upddate.pdf.

Footnotes for Study Calendar 9.1: Pembrolizumab (MK-3475)

- a. Treatment will continue every 3 weeks, with scans after 3 cycles (9 weeks).
- b. Adverse Event Assessments on the study will continue for all patients until 30 days after the last study drug administration. However, patients with ongoing toxicities should be seen more often as clinically indicated.
- c. Post-treatment (after receiving the final dose of pembrolizumab on study) follow-up (prior to progression/relapse): Patients should be seen at 6 weeks (-/+ 1 week) after the last dose, then every 12 weeks (+/- 2 weeks) to the end of the first year after registration, then every 6 months (+/- 4 weeks) to the end of the fifth year after registration.
- d. After progression patients should be followed every 6 months for up to 2 years from the date of treatment registration, then annually thereafter until 5 years from treatment registration.
- e. While on study, blood samples collected for pretreatment laboratory tests may be collected and analyzed no more than 3 days prior to dosing. NOTE: if MK-3475 was delayed per the dose delay/scheduling criteria or if a visit had to be delayed due to major circumstances (such as a health emergency, family/personal emergency, transportation difficulties, scheduling difficulties, a visit date falls on a holiday), the study assessments scheduled for these dates will be delayed.
- f. LDH to be done at screening and at progression/relapse. If patient has a subsequent scan 4 weeks later that does not document progression, following an initial progression while on protocol therapy do not need to have LDH done at this time.
- h. ECG to be performed at baseline, then as clinically indicated.
- i. Women of childbearing potential must have a negative serum or urine pregnancy test within 28 days prior to registration. Following randomization, serum or urine pregnancy tests are required within 72 hours prior to the first dose of study treatment, then according to institutional practice during therapy, tests should coincide with clinic visits for blood work and ending with the discontinuation of study treatment. At discontinuation, a negative pregnancy test within the preceding 6 weeks is sufficient. A pregnancy test should be done at any time there are clinical concerns for possible pregnancy.
- j. Patients with primary melanoma of the head and neck will also require a neck CT.
- k. For patients who have not progressed/relapsed, disease assessments by CT (or MRI if CT cannot be done) chest/abdomen/pelvis or whole body PET-CT will be performed at Week 9 (at end of neoadjuvant therapy) and then imaging studies may be done as clinically indicated at the discretion of the treating investigator.
- o. Thyroid function tests to include TSH, Free T3, and Free T4 must be performed prior to initiating treatment (within 3 days prior to initial dose on Cycle 1) as a reference, should hypothyroidism symptoms arise during treatment. TSH is to be performed prior to dose at week 7, and at initial post treatment follow-up. Additional testing of Free T3 and Free T4 should be performed as clinically indicated if TSH is abnormal or if symptoms are suggestive of thyroid dysfunction.
- p. If a skin lesion is a site of disease, photographs (with a ruler in the photo if the lesion is measurable per RECIST 1.1) must be taken as documentation. Physician's report and photograph must be stored in the patient's chart as source documentation. In addition, the physician's report must be uploaded into Medidata Rave (see Section 14.0). In addition, abnormal lesions concerning for basal cell or squamous cell should be documented in the physician's report and, if biopsy obtained, the pathology report should be included in the patient's chart as source documentation.
- q. See the third bullet under Section 7.1b If after the first disease assessment, the tumor is unresectable, treatment will continue for 1 more cycle and a repeat disease assessment using the same technique as baseline will be obtained 4 weeks later. If at this time the patient's disease is deemed resectable, the patient must continue with resection as previously planned.
- r. History prior to each treatment initiation to include a menstrual, sexual and contraceptive use history, including date of last menstrual period (for women of childbearing potential) which will help determine the need for pregnancy testing. Similar questions regarding contraceptive use should be asked of men who are sexually active with women of childbearing potential. Height is only required at baseline.

Footnotes for Study Calendar 9.1 (contd.): Pembrolizumab (MK-3475)

- s. As the primary endpoint of the study is pCR and the goal of the surgery is to remove visible and microscopic disease, surgery is required for all potentially resectable tumors. If the tumor is deemed unresectable at 9 weeks, a biopsy should be obtained.
- t. Pre-study labs, MRI brain, and ECG should be obtained within 28 days prior to registration.
- u. End of treatment assessment is defined as the first clinical assessment after completion of all pembrolizumab treatments (treatment stopped in preparation for surgical resection). If treatment stopped due to progression, the F/U post progression column would apply. If treatment stopped due to toxicity, the F/U prior to progression would apply.
- v. Survival data are to be collected. Scans obtained in post-treatment F/U post progression, are at the clinical discretion of the treating physician and do not need to be submitted into the EDC system.
- w. Whole blood must be collected prior to protocol treatment (mandatory), but after protocol registration.
- x. Please see Section 15.1 for FFPE submission for translational medicine and Section 15.2 for submission of slides for pathology review.
- * These are the corresponding weeks if there are no dose delays.

